2. SPECIFIC AIMS

Primary Aim: Conduct a pilot randomized clinical trial testing two implementation interventions designed to support delivery of ACHIEVE-D at community-based psychiatric rehabilitation programs.

H1.1. Both the standard and enhanced interventions will increase knowledge of and self-efficacy to deliver ACHIEVE-D, and result in high-fidelity delivery of ACHIEVE-D.

H1.2 Compared to the standard intervention, the enhanced version will lead to greater knowledge, self-efficacy, and ACHIEVE-D fidelity.

Secondary Aims:

1. Assess the acceptability, appropriateness, and feasibility of the adapted ACHIEVE curriculum to coaches, peer leaders, program directors and other staff.
2. Assess consumer outcomes of self-reported diet and physical activity, weight, attendance and satisfaction.

This study will lead to a refined intervention that will contribute to the future development of a certified ACHIEVE-D training program for mental health staff and peers, and thus facilitate future widespread dissemination of an evidence-based behavioral weight-loss program for individuals with SMI.

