4. DESIGN SUMMARY

The core design is a randomized, two-arm, parallel, pilot clinical trial where 10 psychiatric rehabilitation program sites will be randomized to a 6-month standard or enhanced intervention. This trial will recruit and enroll participants at each site – staff, peer leaders, and mental health consumers, (Figure 1). The primary outcome variables will be coaches' knowledge, self-efficacy, and fidelity to the ACHIEVE curriculum.

Figure 1. Study Populations with Corresponding Activities and Outcomes for Each Site

We estimate up to 280 mental health organization staff and peer leaders will participate in data collection including program directors, coaches, and other psychiatric rehabilitation program staff. Two coaches and one peer leader per study site will be randomized to the standard or enhanced intervention. Up to 120 mental health consumers across all sites will be enrolled, and all will receive group weight-management sessions delivered by the trained coaches at their site.

The ACHIEVE-D curriculum is designed to fit into and will be part of the regular psychiatric rehabilitation programming that is already being conducted.

Randomized groups:

Standard intervention: At those sites assigned to the standard group, two staff and one peer will receive training and approximately 8-12 consumers with SMI will participate in the ACHIEVE weight loss program. The standard intervention will combine onboarding training, ongoing online training, and online avatar-assisted motivational interviewing practice^{19,20} for all coaches, as well as organizational strategy meetings to garner the leadership support for ACHIEVE implementation²¹.

Enhanced intervention: At those sites assigned to the enhanced group, the implementation intervention will include all standard strategies and will add performance coaching for the coaches.

Trainings and meetings will be remote during the COVID-19 pandemic.

We outline the eligibility criteria sites in Section 5. Then, we describe the eligibility criteria as well as data collection and measurements for each study population separately in Sections 6-8.

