6.3 Measurements

Measurements for coaches and peer leaders will be conducted using standardized operating procedures and quality control methods. Specific study forms (RedCap or paper) will be used to collect data.

Primary Outcomes

Knowledge of the ACHIEVE curriculum. We will assess knowledge about key elements of the ACHIEVE curriculum using two measures: A 22-item *ACHIEVE Curriculum Weight Management Knowledge* measure and a 16-item *ACHIEVE Curriculum Exercise Knowledge* measure. The study team created these questions

using best practices recommended by the National Board of Medical Examiners for item writing⁵⁶. These measures will be assessed at baseline and 6 months.

Self-efficacy to deliver the ACHIEVE curriculum. We will assess self-efficacy to deliver key elements of the ACHIEVE curriculum, where participants rate their confidence to deliver each element on a 10-point scale. The study team used principles from other related self-efficacy measures in creating our measure^{57,58}. This measure will be assessed at baseline and 6 months. Given that this type of self-report measure may be subject to response shift bias^{59,60}, we will also have coaches reflect upon their baseline ability to carry out these elements at the 6-month point, which will enable us to determine whether response shift bias may be present.

Fidelity to the ACHIEVE curriculum (ACHIEVE fidelity video assessment form and ACHIEVE fidelity documentation assessment form). To determine fidelity to the curriculum, we will use two data sources. First, coaches will video-record two ACHIEVE group sessions each month at each site, one per coach. Two study team members will view each recording and use a rating tool to assess fidelity to key elements of the ACHIEVE curriculum. We will calculate inter-rater reliability between coders. Second, a study team member will examine documentation practices of the coaches on the same day that video tapes are obtained. The study team has identified elements from both data sources that will be summed to create a composite score. Numerical values from all items will be used. For Y/N items, 'Yes' will equal a numerical score of 2 and 'No' a numerical score of 1.

Other Measures

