7.3 Measurements

Measurements will be conducted using standardized operating procedures and quality control methods. Specific study forms either in RedCap or paper will be used to collect data.

Table 5. Data Collection Schedule for Consumers

		Follow-up
--	--	-----------

	Screening/ Baseline	During	6M Post
General Assessments			
Evaluation to Give Consent	x		
Demographics	x		
Exercise pre-participation screening (modified 2018 PAR-Q)	x		
Medical history	x		
Medications	x		x
Readiness rulers	x		
Physical Measurements			
BMI	x		x
Blood pressure	x		
Physical Activity			
CARDIA/EARLY Q – sedentary behavior	x		x
Diet			
Block Dietary Fat Q	x		x
Block Dietary Fruit/Vegetable Q	x		x
EARLY Eating Away from Home Q	x		x
EARLY SSB Consumption Q	x		x
NHIS Screener	x		x
Satisfaction			
Consumer Satisfaction & Helpfulness Q			x
Other Measures			
Palatable Eating Motives Scale (PEMS) – Coping Subscale	x		x
Reward-based Eating Drive (RED) Scale	x		x
Important Others Q	x		x
Medical Events			x
Perceived Stress Scale (PSS)	x		x
Ambulatory Screening for COVID-19	x		x

General Assessments

Demographics. We will collect demographic information such as age, sex, race, and ethnicity. We will also assess how often they attend the program.

We will use several measures and data sources to assist in determining eligibility for the study. **Exercise pre-participation screening (modified 2018 PAR-Q):** This modified physical activity readiness questionnaire will be used to assess if consumer is able to participate in exercise classes. **Medical History:** We will collect medical history information from each consumer to assess ability to participate in the ACHIEVE program and the staff. **Medications:** We will list all of the consumer's current medications. We will use the *Readiness Rulers* survey to assess participant's readiness to lose weight and willingness to participate in the ACHIEVE program.

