10. RANDOMIZATION AND BLINDING

Following baseline data collection, sites will be randomized to the standard or enhanced arms. Randomized blocks of 2 in random order will be used to create the randomization sequence. The random sequence and allocation groupings will be stored in RedCap, only the data analyst will distinguish the treatment assignment to sites. Due to the nature of the intervention, both participants and interventionists will be aware of the assignment. Data collectors measure study outcomes. Investigators, staff and participants are masked to outcome data, with the exception of trial statistician, study coordinator, data analyst and independent study monitor.

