11.2 Standard Intervention Group

The standard intervention components are described in Exhibit 2. Staff Coaches and Peer Leaders will participate in all trainings.

Exhibit 2. Overview of Standard Intervention Components		
	Component	Elements
Standard	On-Board Training	During training sessions, a mix of didactic content and role play are used. Materials needed to implement all components the ACHIEVE weight-loss curriculum is covered. More detail on how to discuss each weight-loss subject is introduced in a stepwise fashion. Training on motivational interviewing (MI) techniques is also provided. Master trainers who have expertise in health coaching and MI training conduct the initial on-board training.
	Online Training Modules	Monthly online didactic training modules (15-20 min) are an efficient method for coaches to observe and learn how to deliver the ACHIEVE weight-loss topics. Each training module includes both relevant didactic content and examples of experienced ACHIEVE staff providing real-world examples of delivering the content in groups. Coaches view the online modules each month before teaching that specific component of the program.
	Online Avatar MI Practice Module	At the end of the on-board training, coaches are given access to an online avatar MI practice module, which includes a 15-minute didactic component and 15-minute virtual practice conversations with consumers with SMI. These simulated conversations allow coaches to practice (a) providing feedback about weight-loss progress and (b) increasing participant engagement in exercise classes. The avatar module includes built-in MI performance feedback. Coaches are encouraged to use the module weekly for the first three months and as needed (e.g., monthly), repeating practice until they receive a "good" score.

Our training approach provides interactive opportunities for coaches to practice the skills needed to implement the ACHIEVE curriculum, a strategy more effective than didactic education.

At minimum, each Coach will be video-recorded delivering an ACHIEVE group during months 1, 3 and 6; each coach may be recorded monthly. These recordings will be for research purposes only and will not be shared with the site supervisors. Recordings will be shared with master trainers on the study team who are responsible for assessing fidelity to the ACHIEVE curriculum (master trainer grading will not be used in outcome scoring).

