13. DATA ANALYSIS

We will assess the effects of the implementation intervention on providers' knowledge self-efficacy, and fidelity to the ACHIEVE curriculum, as well as consumer outcomes using generalized linear mixed-effects models under the intent-to-treat approach. Mean models will include a binary intervention group indicator, time indicators, intervention by time interaction terms, and fixed effects for the 10 study sites. The time indicator coefficients estimate time-specific mean outcome changes in the "standard" group and interaction coefficients estimate the between-arm differences of time-specific outcome changes from baseline. The linear combination of these time-specific coefficients captures the time-specific mean outcome changes in the "enhanced" group. The model will use an unstructured variance covariance matrix for the repeated outcome measurements over time within individuals. To assess whether knowledge and self-efficacy mediate implementation intervention

effects, we will estimate the magnitude of attenuation on intervention effects in the consumer outcome models with vs. without these measures. We will also examine potential moderators, e.g. study sites' implementation intervention fidelity and/or implementation climate, by adding appropriate interaction terms to the models. We will analyze survey data on our implementation measures prior to conducting focus groups in order to explore survey findings in depth (e.g., if providers' rate performance coaching as having mediocre acceptability, we will explore reasons why in the focus groups). We will use descriptive statistics to analyze survey measures of perceptions of acceptability, feasibility and appropriateness of implementation intervention and ACHIEVE-D. Point estimates and corresponding 95% confidence intervals will be obtained.

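### With fixed effects for all 10 randomised sites, the planned model cannot estimate the between-arm difference in fidelity level (a primary outcome), nor any arm contrast in consumer satisfaction

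*Combined protocol and SAP*

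**What the plan says.** Section 4 makes the site the unit of randomisation: "10 psychiatric rehabilitation program sites will be randomized to a 6-month standard or enhanced intervention". Section 10 adds that randomisation follows baseline data collection and that "Randomized blocks of 2 in random order will be used to create the randomization sequence". Each site therefore lies wholly in one arm, and 10 sites give 5 against 5.

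Section 4 names coaches' knowledge, self-efficacy and fidelity as the primary outcome variables. Hypothesis H1.2 in Section 2 reads: "Compared to the standard intervention, the enhanced version will lead to greater knowledge, self-efficacy, and ACHIEVE-D fidelity". H1.1 expects high-fidelity delivery in both arms.

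Section 13 covers these outcomes and the consumer outcomes with a single specification: "Mean models will include a binary intervention group indicator, time indicators, intervention by time interaction terms, and fixed effects for the 10 study sites". It takes the treatment effect from the interactions: "interaction coefficients estimate the between-arm differences of time-specific outcome changes from baseline". The only correlation structure it describes is for repeated measures within individuals. It states no random site effect and no constraint on the site effects.

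The measurement schedules are as follows.

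- **Fidelity:** Table 2 marks both ACHIEVE fidelity forms only in the column for the delivery period. Section 6.3 says "First, coaches will video-record two ACHIEVE group sessions each month at each site, one per coach", while Section 11.2 says "At minimum, each Coach will be video-recorded delivering an ACHIEVE group during months 1, 3 and 6; each coach may be recorded monthly".
- **Consumer satisfaction:** Table 5 marks "Consumer Satisfaction & Helpfulness Q" at 6 months only.
- **Attendance:** Section 7.3 lists it as a process measure collected while the curriculum runs.
- **Knowledge and self-efficacy:** both are measured at baseline and 6 months.

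**The concern.** The model identifies arm effects only through change from a pre-randomisation baseline. Fidelity, attendance and satisfaction have no such baseline. Fidelity cannot have one, because it is scored from sessions that are delivered after randomisation.

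For fidelity, the only contrast left is differential change since the first recording, whereas H1.2 is about which arm has the higher fidelity. Performance coaching is the sole difference between the arms, and Section 11.3 lists curriculum fidelity as the first purpose of its feedback. The hypothesis closest to what the trial varies is therefore the one the model cannot answer.

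There is also a practical risk. If software resolves the redundancy by dropping a site dummy, the output still shows an intervention coefficient. Its value depends on which dummy was dropped, and a reader could take it for the treatment effect.

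**Working it through.** The documents give no sample-size or power figure for this point, so there is nothing to reproduce. The question is which contrasts the stated mean model identifies.

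**Inputs.** 10 sites, randomised as sites (Section 4); 5 per arm, which follows from blocks of 2 (Section 10); 2 coaches per site (Sections 1 and 4); up to 120 consumers (Section 4), so 120 / 10 = 12 per site; mean model from Section 13.

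**Step 1: the alias.** Let A be the arm indicator and S_j the indicator for site j. Arm is constant within site, so A = sum of S_j over the five enhanced sites. The arm column is an exact linear combination of the site columns.

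**Step 2: columns and rank.** With T time points the columns are 1 (intercept) + 1 (arm) + (T − 1) (time) + (T − 1) (arm × time) + 9 (site dummies) = 9 + 2T.

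| Outcome | T | Columns | Rank | Arm difference in level | Arm × time |
|---|---|---|---|---|---|
| Satisfaction, or one fidelity composite per coach | 1 | 11 | 10 | not estimable | does not exist |
| Knowledge, self-efficacy, weight, diet (baseline, 6 months) | 2 | 13 | 12 | not estimable | estimable |
| Fidelity, months 1, 3, 6 | 3 | 15 | 14 | not estimable | estimable, relative to month 1 |
| Fidelity, monthly | 6 | 21 | 20 | not estimable | estimable, relative to month 1 |

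In the two multi-recording fidelity rows, the arm difference is not estimable at any month, nor averaged over months. In the knowledge row the interaction is the intended effect, so those outcomes are unaffected.

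**Step 3: what the interactions return for fidelity.** Each interaction equals the arm difference at that month minus the arm difference at month 1.

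- Constant advantage of 10 points at months 1, 3, 6: 10 − 10 = 0 and 10 − 10 = 0. The same holds for any constant size.
- Growing advantage of 1, 3, 6: 3 − 1 = 2 and 6 − 1 = 5. The month-1 part is lost.

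**Step 4: the coefficient printed if one enhanced-site dummy is dropped.** For a single time point it equals the mean of the enhanced site whose dummy was dropped minus the mean of the standard reference site. The weights are +1 and −1, with 0 on the other eight sites. That compares 2 coaches with 2 coaches instead of 10 with 10.

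With months 1, 3 and 6, the weights on the site-by-month means (coaches averaged) are:

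- the two reference sites: ±0.467 at month 1 and ±0.267 at each later month, which sum to ±1 within site after rounding;
- the other eight sites: 0.133 in magnitude at month 1 and 0.067 with opposite sign at months 3 and 6, which sum to 0 within site after rounding.

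As an illustration, take a true advantage of 10 and let three enhanced sites deviate from the standard reference site by 0, −4 and +6. The printed coefficient is 10 + 0 = 10, 10 − 4 = 6 or 10 + 6 = 16, depending only on which of the three dummies is dropped.

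**Step 5: the same model without site fixed effects.** The columns become 2T and the matrix has full rank: 2 of 2 (T = 1), 6 of 6 (T = 3), 12 of 12 (T = 6). The arm difference at each month, and averaged over months, is then estimable. Inference rests on 10 − 2 = 8 degrees of freedom, with t = 2.306.

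In SD units, SE = √[(2/5)(ρ + (1 − ρ)/m)], where m is the number of people per site with one value each and ρ is the intraclass correlation. The documents give no ρ, so I assume a range of 0 to 0.5.

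- Coaches, m = 2: SE 0.447 to 0.548, so the 95% CI half-width is 2.306 × SE = 1.03 to 1.26 SD.
- Consumers, m = 12: SE 0.183 to 0.465, half-width 0.42 to 1.07 SD.

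**The case against.** The strongest reply is that differential change in fidelity is estimable and informative. The arms share onboarding, online modules, avatar practice and strategy meetings. They differ only by roughly monthly performance coaching, so at the first recording they may differ by one session at most. If the advantage builds up, the month-6 interaction captures most of it: 5 of 6 units in the growing example above. The result of exactly 0 needs the whole advantage to be present at month 1 and never to grow.

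That limits the loss under some patterns but does not restore the hypothesis. Month 1 is after randomisation, and nothing schedules that recording before the first coaching session. Change since month 1 is neither the change from baseline that Section 13 describes nor the level difference in H1.2. It also says nothing about H1.1, and satisfaction has no second time point.

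An analyst could instead constrain the site effects to sum to zero within each arm and so recover an arm estimate. The plan does not say this, and it leaves between-site variation out of the standard error. In 20,000 simulated trials, the two-sided 5% type I error was then 6.1% to 9.7% with 2 people per site and 12.5% to 32.5% with 12, for assumed intraclass correlations of 0.05 to 0.20. A comparison of site means stayed at about 5%.

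Three points on the other side stand. The 2-against-2 reading is exact only for a single time point; with three recordings it holds for the net site weights. Satisfaction and attendance are secondary, and H1.2 does not name them. Knowledge and self-efficacy are not affected. That the trial is a pilot does not change the conclusion, because a pilot estimate must also be identifiable.

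**Conclusion.** The concern holds. Under the model as written, the between-arm difference in fidelity level that H1.2 states is not estimable at any month or averaged over months, and no arm contrast in consumer satisfaction is estimable. Attendance has no baseline either, so its level difference is equally unidentified.

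This follows from randomisation by site, fixed effects for all 10 sites and the measurement schedules. It needs no assumed effect size, variance or intraclass correlation; only the interval widths and type I error rates rest on assumed correlations. One of the three primary outcomes therefore has no working analysis for its between-arm hypothesis, and this should be corrected before fidelity is compared by arm.

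**What to change.** For outcomes without a pre-randomisation baseline (fidelity composite, attendance, satisfaction), Section 13 should:

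1. Remove the 10 site fixed effects and use a random site intercept, with coach nested in site for fidelity.
2. Define the fidelity estimand as the enhanced-minus-standard difference in mean composite score, either averaged over months 1, 3 and 6 or at month 6, and say which is primary.
3. Use a small-sample correction giving about 8 degrees of freedom for the arm contrast. A comparison of the 10 site means on 8 degrees of freedom is a simple alternative; it is equivalent when recordings are balanced and complete.
4. Score fidelity from the same recording months in both arms, and reconcile the monthly schedule in Section 6.3 with the months 1, 3 and 6 minimum in Section 11.2.
5. Report each arm's mean composite with its 95% confidence interval, which addresses H1.1.

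The arm-by-time contrast for knowledge, self-efficacy and other outcomes with a baseline can stay on this point.

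The cost is a change of wording, with no new data. Confidence intervals will be wide because they reflect 5 sites against 5.

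### Knowledge and self-efficacy: a common baseline mean with site-level error terms would be a cheap improvement on the change-score contrast planned in section 13, with an uncertain gain and a small possible loss

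*Combined protocol and SAP*

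**What the plan says.** Section 13 specifies the mean structure: "Mean models will include a binary intervention group indicator, time indicators, intervention by time interaction terms, and fixed effects for the 10 study sites". It adds: "The model will use an unstructured variance covariance matrix for the repeated outcome measurements over time within individuals". The arm effect is read from the interaction ("interaction coefficients estimate the between-arm differences of time-specific outcome changes from baseline"). The section names the model family but no link, no random site or site-by-time term, no degrees-of-freedom method and no baseline adjustment.

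Section 6.3 gives two time points for both outcomes. For knowledge: "These measures will be assessed at baseline and 6 months". For self-efficacy: "This measure will be assessed at baseline and 6 months". Table 2 agrees. The text of section 6.2 also mentions follow-up at 3 months, which does not fit Table 2 and should be reconciled.

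Section 10 fixes the order of events: "Following baseline data collection, sites will be randomized to the standard or enhanced arms". On who may see what, it says "Investigators, staff and participants are masked to outcome data, with the exception of trial statistician, study coordinator, data analyst and independent study monitor", and, of the allocation, "only the data analyst will distinguish the treatment assignment to sites".

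**The concern.** Two separate matters meet in one model.

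The first is efficiency. Baseline is measured before allocation, so both arms have the same expected baseline mean. The planned model leaves baseline means free by arm and site and so cannot use that. With few units, a chance baseline difference is then subtracted in full, whether or not baseline predicts the 6-month value that strongly.

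The second is the error term. Sites are randomised, but a site effect that is constant over time cancels out of every change score. If sites differ in how much their coaches change, the planned error term does not contain that variation.

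Knowledge and self-efficacy are two of the three primary constructs in section 4, and H1.2 compares the arms on them with two coaches in each of 10 programs. The baseline data are collected anyway, so better use of them needs no new data.

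**Working it through.** **Inputs from the documents.** 10 sites, blocks of 2 (so 5 per arm), 2 coaches per site (20 coaches), baseline and 6 months. The documents give no SD, correlation, effect size, power or precision target, so there is no planned figure to reproduce.

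**Assumed inputs.** Correlation ρ of 0.3, 0.5, 0.7 and 0.85. SD ratio k (6-month SD divided by baseline SD) of 0.7, 1, 1.5 and 2. Site share of variance 0 or 0.1. Site-by-time share 0 or 0.1.

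**Step 1: what the planned term estimates.** The section 13 mean model (arm, 10 site indicators, time, arm-by-time) has 13 columns and rank 12, because the site indicators span arm. Generalised least squares gives each of the 10 enhanced-arm coaches a weight of −0.1 at baseline and +0.1 at 6 months under every covariance tried. That is the raw difference in mean change. Removing only the arm column leaves these weights and the variance unchanged. Complete data are needed: in one example with three 6-month values missing, the model gave −0.116 against −0.155 from completers.

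**Step 2: gain from a common baseline mean, covariance known, no site effects.** The best baseline weight is ρk instead of 1. The variance relative to the planned contrast is

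1 − (1 − ρk)² / (1 + k² − 2ρk).

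For ρ = 0.3, k = 1: 1 − 0.49/1.40 = 0.65. For ρ = 0.5, k = 0.7: 1 − 0.4225/0.79 = 0.47.

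| k | ρ=0.3 | ρ=0.5 | ρ=0.7 | ρ=0.85 |
|---|---|---|---|---|
| 0.7 | 0.42 | 0.47 | 0.49 | 0.45 |
| 1 | 0.65 | 0.75 | 0.85 | 0.93 |
| 1.5 | 0.87 | 0.96 | 1.00 | 0.89 |
| 2 | 0.96 | 1.00 | 0.93 | 0.69 |

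The ratio never exceeds 1, and equals 1 where ρk = 1.

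**Step 3: the same with the covariance estimated from 20 coaches.** The model proposed under the fix was fitted by REML in 48 simulated settings of 2,000 trials each (Monte Carlo SE of the ratio at most 0.021). Variance ratios, over all ρ and site shares:

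- k = 0.7: 0.45 to 0.55
- k = 1: 0.72 to 0.97 (0.72, 0.78, 0.90, 0.96 by ρ with no site effects)
- k = 1.5: 0.90 to 1.07
- k = 2: 0.70 to 1.07

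The largest loss is 7% in variance, or √1.07 = 1.03, about 3% to 4% in SE. Coverage of the nominal 95% interval with 8 df was 93.7% to 97.5% for k up to 1.5, with a minimum of 92.6% at k = 2, ρ = 0.85 and site-by-time variance. The simulated site effects scaled with the SD at each time, so the fitted site structure is slightly wrong when k is not 1.

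**Step 4: the clustering question, kept separate.** Take k = 1, a site-by-time share of 0.1 at each time, and total correlation ρ. In units of the outcome variance, a coach's change has variance 2(1 − ρ), of which 2 × 0.1 is shared within site. The within-site correlation of change is therefore 0.1/(1 − ρ).

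| ρ | Within-site correlation of change | Coverage, coach-level interval (18 df assumed) | Coverage, proposed model (8 df) |
|---|---|---|---|
| 0.3 | 0.14 | 92.6% | 95.6% |
| 0.5 | 0.20 | 92.8% | 95.4% |
| 0.7 | 0.33 | 90.6% | 95.2% |
| 0.85 | 0.67 | 85.6% | 94.4% |

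The last row is an extreme: it needs two coaches' changes at one site to correlate at 0.67.

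**Step 5: interval width at k = 1.** Site-based df are 10 − 2 = 8; coach-level df are 20 − 2 = 18. The t quantiles are 2.306 and 2.101, a factor of 1.10. Against the coach-level interval the proposed one has relative width 0.92, 0.98, 1.05, 1.09 by ρ with no site effects, and 0.95, 1.02, 1.14, 1.35 with a site-by-time share of 0.1. Against the planned contrast on 8 site-based df, the widths are 0.85, 0.91, 0.97, 1.02 and 0.82, 0.87, 0.90, 0.93.

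**The case against.** The planned contrast is clearly defined and valid under randomisation. This is a pilot with no stated precision target. Every size above rests on assumed correlations and SDs, and the range runs from halving the variance to a 7% rise. The change is also more than deleting one term: it replaces the site effects and adds two random effects in a model for 20 people. When the true site-by-time share was 0, its variance was estimated as zero in 51% to 68% of runs. All of that stands. It is why this is an option to weigh and not a defect.

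The base of 20 is also open. Section 4 speaks of coaches, but Table 2 and section 6.3 apply these measures to peer leaders too, and section 13 refers to providers. With one peer leader per site the analysed number would be 30, and the figures would change. No missing-data or ceiling-limited setting was simulated.

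Timing is a fair doubt. The current version is dated January 2025 and its change list already deals with interviews after project completion. Section 9 has outcome distributions monitored by site. This suggests, without proving it, that a change before outcome data are seen may no longer be possible.

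Three stronger readings are tempting and not supported. A reader might infer that the planned estimate is biased; it is not. A reader might take the coverage of about 86% as what to expect; it belongs to the extreme within-site correlation of 0.67, and the plan states neither that correlation nor the 18 df. A reader might expect a narrower reported interval; Step 5 shows it may be wider.

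**Conclusion.** The point holds as a cheap improvement for knowledge and self-efficacy, with medium confidence. Given complete data and an identity link, the planned arm effect is the raw difference in mean change and leaves pre-randomisation baseline information unused. For assumed correlations of 0.3 to 0.85 and 20 coaches, a common baseline mean lowers the variance of the arm effect by roughly 3% to 30% at equal SDs and by about half at k = 0.7. It gives no gain where ρk is near 1, and can cost up to about 7% at k of 1.5 to 2. Bounded scales with both arms rising could shrink the 6-month SD, but a floor at baseline would do the opposite, so the direction is a judgement.

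Separately, if sites differ in change, a coach-level interval is too narrow. With a site-by-time share of 0.1 at equal SDs, coverage is about 93% at ρ of 0.3 to 0.5 and about 91% at 0.7. This is a correction for randomisation by site, not part of the efficiency gain.

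Nothing is claimed for fidelity, which has no baseline, or for consumer outcomes.

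**What to change.** In section 13, for knowledge and self-efficacy only:

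- Drop the arm main effect, so that there is one common baseline mean, and keep time and arm-by-time. H1.1's within-arm changes still come from these terms.
- Replace the 10 site fixed effects with random site and site-by-time effects. Without this step, dropping the arm term changes nothing.
- Keep the unstructured within-person covariance, and use 8 site-based df even when the site-by-time variance is estimated as zero.
- Use the prospective baseline, not the self-efficacy recall taken at 6 months.
- State the link, say whether peer leaders are analysed with coaches, and reconcile the 3-month wording in section 6.2 with Table 2.
- Make the change in a dated amendment before any outcome table by arm exists, and report the planned change-score contrast as a sensitivity analysis. If results by arm have already been seen, keep the planned contrast as the main analysis and report this one as supplementary. The date matters because section 10 exempts the statistician and data analyst from outcome masking and lets the analyst know the allocation.

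An ANCOVA on site means (7 df) is a weaker fallback. It loses precision above a correlation of about 0.7 at equal SDs, and its variance ratio is 1.00 to 1.17 at k = 1.5.

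The cost is a rewrite of the site terms and no new data. The price is the possible 7% rise in variance and an interval that may be wider than a coach-level one, because it reflects randomisation by site.
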